Dates of Analytical Portion :

Method Validation : December 2018
Sample Analysis : After completion of Period 1 and 2

Objectives

The objective of this study is to investigate whether 2 mg cyproterone acetate and 0.035 mg ethinyl estradiol film-coated tablet (**Elzsa[®]**) manufactured by PT. Sydna Farma is bioequivalent to its reference product, Diane[®]-35 sugar-coated tablet manufactured by Bayer Weimar GmbH, Germany for Bayer Pharma AG, Germany, **imported by PT. Bayer Indonesia, Depok, Indonesia.**

PharmaMetric Labs**Study Centre, Clinical Study Laboratory, Analytical Laboratory, Pharmacokinetics and Statistical Analysis Laboratory:**

PT. Pharma Metric Labs
 [name]
 [name]
 [name]
 Indonesia
 [contact]
 [contact]

Medical Screening (blood and urine) Laboratory:

Pramita Clinical Laboratory
 [name].
 [contact]
 [contact]

Sponsor

PT. Sydna Farma
 [name]
 [name]
 Indonesia
 [contact]
 [contact]

Study design

Randomized, single blind, two period, single dose, cross-over study with three weeks washout period in 24 healthy female subjects under fasting condition.

The overall clinical study requires approximately 8 weeks to be completed. The drug allocation information is limited to the Data Management Officer only.

If the above study results in the conditions below, the study could be continued to the second stage with a minimum 12 subjects addition. The second stage study's pharmacokinetics will be statistically analyzed within 94.12% confidence interval. The conditions are:

1. The first stage study has demonstrated bioequivalence, but the number of subjects is not adequate to fulfill 80% power study calculated from the intra subject CV of AUC_t obtained; OR
2. The first stage study has resulted in non-bioequivalence but the geometric mean ratio of the AUC_t falls within 90-110%, and it is probable to have bioequivalence result if the study is continued to the second stage.

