are collected from fresh clean venipuncture using disposable sterile syringe and needle. Collected blood samples are centrifuged at 3000 rpm for 10 minutes using 32-cm rotor diameter centrifuge. Separated plasma is then stored frozen at a maximum temperature of -20°C until assayed.

Standardized meals are served 4 hours after drug administration. A record of the menu served and meal taken by subjects at every study period will be maintained.

After a washout period of three weeks, the study will be repeated in the same manner with the alternate drug.

The subjects' safety is monitored during the entire study. They are under direct supervision by Study Physician at the study site. Vital signs (blood pressure, pulse, respiration rate and body temperature) are monitored and recorded in the Case Report Form.

Analytical Procedures

Plasma concentration of cyproterone acetate and ethinylestradiol will be measured by a validated LC-MS/MS method.

Plasma containing cyproterone acetate and ethinyl estradiol is spiked with internal standard solution and blended well. The drug is then extracted using an organic solvent. The organic layer is transferred to a clean glass tube and evaporated to dryness under nitrogen stream in a water bath. The residue is then reconstituted with organic solvent and an aliquot is injected into the LC-MS/MS system. The LLOQ is 0.4 ng/ml and 4.99 pg/ml for cyproterone acetate and ethinylestradiol, respectively.

Statistical Procedures

The area under the cyproterone acetate and ethinylestradiol concentration versus time curve from 0 to 72 hours (AUC_t) is then calculated using trapezoidal rule. Bioequivalence of the two formulations will be assessed by comparing the AUC_t and C_{max} of cyproterone acetate and ethinyl estradiol values after ln transformation of the concentration data. The geometric mean ratios (test/reference) of the ln-transformed data and their 90% confidence intervals will be further analyzed with a parametric method (analysis of variance/ANOVA) using Equiv Test[®] version 2.0 (Statistical Solution Ltd., Saugus, MA, USA), or manual calculation which has been validated to Equiv Test[®].

Bioavailability Parameters and Bioequivalence Criteria

The two products are considered bioequivalent when the 90% confidence intervals of the cyproterone acetate and ethinyl estradiol geometric mean ratio between test and reference product fall within the range of 80.00-125.00% for AUC_t and C_{max} .

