Ethinylestradiol serum levels decrease in two phases, the terminal disposition phase is characterised by half-life of approximately 24 hours. Unchanged drug is not excreted, ethinylestradiol metabolites are excreted at a urinary to biliary ratio of 4:6. The half-life of metabolite excretion is about 1 day.

A bioequivalence study to compare the test product, 2 mg cyproterone acetate/0.035 mg ethinylestradiol fixed-dose tablets and the reference product Diane 35[®] (2 mg cyproterone acetate/0.035 mg ethinylestradiol fixed-dose tablets, Schering France), was performed. The study design was two-way, open, randomised, cross-over study in 35 female postmenopausal healthy volunteers (aged 35-65 years) after single oral dose. The study was clinically well tolerated. The pharmacokinetic parameters of ethinylestradiol are illustrated in Table I and the parameters of cyproterone acetate in Table II.

Table I. Pharmacokinetic parameters of ethinylestradiol

Pharmacokinetic parameters of ethinylestradiol (n=30)			
	Test product	Diane 35 [®]	90% CI
AUC _{0-t} (pg.h/ml)	2044.34 ± 761.49	2026.55 ± 612.80	92.21 – 104.66
AUC _{0-∞} (pg.h/ml)	2274.67 ± 849.00	2229.15 ± 682.69	93.40 – 106.27
C _{max} (pg/ml)	169.23 ± 52.09	177.49 ± 58.72	91.94 – 100.29
t _½ (h)	16.07 ± 4.76	16.82 ± 5.39	
t _{max} (h)	2.0 ± 0.75	2.00 ± 0.50	

Table II. Pharmacokinetic parameters of cyproterone acetate

Pharmacokinetic parameters of cyproterone acetate (n=30)			
	Test product	Diane 35 [®]	90% CI
AUC _{0-t} (pg.h/ml)	318206.1 ± 78626.9	327887.3 ± 85063.0	94.08 – 100.15
AUC _{0-∞} (pg.h/ml)	403149.9 ± 116224.5	428492.9 ± 132888.0	90.70 – 97.75
C _{max} (pg/ml)	27436.24 ± 5872.79	29942.10 ± 7268.07	86.23 – 97.63
t _½ (h)	103.56 ± 24.84	116.81 ± 38.68	
t _{max} (h)	2.00 ± 0.00	1.50 ± 0.50	

A bioequivalence pilot study to compare the test product, 2 mg cyproterone acetate/0.035 mg ethinylestradiol fixed-dose tablets manufactured by PT. Sydna Farma, and the reference product, Diane 35[®] fixed-dose tablets manufactured by Bayer Weimar GmbH, Germany for Bayer Pharma AG, Germany), was performed in 6 healthy female subjects at PT. Pharma Metric Labs, Jakarta. The pharmacokinetic parameters of ethinylestradiol are illustrated in Table III and the parameters of cyproterone acetate in Table IV.

Table III. Pharmacokinetic parameters of ethinylestradiol of the bioequivalence pilot study

Pharmacokinetic Parameter		Test Drug (Lydia [®]) (n = 6) mean (SD)	Reference Drug Diane [®] -35 (n = 6) mean (SD)

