8. INVESTIGATIONAL PLAN

8.1. Study design

Randomized, single blind, two period, single dose, cross-over study with three weeks washout period in 24 healthy female subjects under fasting condition.

The overall clinical study requires approximately 8 weeks to be completed. The drug allocation information is limited to the Data Management Officer only.

If the above study results in the conditions below, the study could be continued to the second stage with a minimum 12 subjects addition. The second stage study's pharmacokinetics will be statistically analyzed within 94.12% confidence interval. The conditions are:

1. The first stage study has demonstrated bioequivalence, but the number of subjects is not adequate to fulfill 80% power study calculated from the intra subject CV of AUC_t obtained; OR
2. The first stage study has resulted in non-bioequivalence but the geometric mean ratio of the AUC_t falls within 90-110%, and it is probable to have bioequivalence result if the study is continued to the second stage.

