8.5. Statistical evaluation

Bioequivalence of the two drug formulations is assessed by calculating individual AUC_t and C_{max} values. The mean ratio (test/reference) of the ln-transformed data and their 90% confidence intervals is analyzed with a parametric method (analysis of variance/ANOVA) using Equiv Test[®] version 2.0 (Statistical Solution Ltd., Saugus. MA, USA) or manual calculation which has been validated to Equiv Test[®]

90% confidence intervals (90% CIs) are calculated using the following equation :

$$(90\% \text{ CI})_{diff} = \text{difference} \pm t_{0.1 (n-2)} \times SE_{diff}$$

$$\text{difference} = \text{mean of ln T} - \text{mean of ln R}$$

PharmaMetric Labs

n = number of subject

$\alpha = 0.05$

$SE\ diff = (\frac{1}{2}MS_{residual} \times (1/nTR + 1/nRT))^{\frac{1}{2}}$

(90% CI) ratio = anti ln (90% CI)_{diff} X 100%

The two products are considered bioequivalent when the 90% confidence interval of the cyproterone acetate and ethinyl estradiol geometric mean ratio between test and reference product falls within the range of 80.00 - 125.00% for AUC_t and C_{max}.

If a pre-dose concentration of cyproterone acetate and ethinyl estradiol is detected, the subject's data can be included in the pharmacokinetic and statistical analysis without adjustment, if the pre-dose concentration is equal to or less than 5% of the C_{max} value of the corresponding period. If the pre-dose concentration is greater than 5% of the C_{max} value, the subject's data will be dropped from all pharmacokinetic and statistical evaluations of cyproterone acetate and ethinyl estradiol.

Subjects who lack of any measurable concentrations, or have only very low plasma concentrations of cyproterone acetate and ethinyl estradiol for the reference medicinal product, will be excluded from statistical analysis. According to EMA Guidance (CPMP/EWP/QWP/1401/98 Rev.1/Corr**), a subject is considered to have very low plasma concentrations if its AUC is less than 5% of reference medicinal product geometric mean, calculated without inclusion data from the outlying subject. Data (concentrations and pharmacokinetic parameters) from these excluded subjects will be presented but excluded from descriptive statistics. If the study is continued to the second stage, the 94.12% confidence intervals (94.12% CIs) are calculated using $\alpha = 0.0294$.

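### Does the second-stage rule leave a Cmax failure without a workable criterion?

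*Combined protocol and SAP*

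**What the plan says.** Section 8.1, repeated in the synopsis under Study design, describes a "cross-over study with three weeks washout period in 24 healthy female subjects under fasting condition". It then states that "the study could be continued to the second stage with a minimum 12 subjects addition" in either of two cases.

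- **Condition 1.** Stage 1 shows bioequivalence, but the number of subjects falls short of "80% power study calculated from the intra subject CV of AUC_t obtained".
- **Condition 2.** Stage 1 does not show bioequivalence, but "the geometric mean ratio of the AUC_t falls within 90-110%, and it is probable to have bioequivalence result if the study is continued" to a second stage.

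Section 8.5 and the synopsis criteria define bioequivalence as the intervals for AUC_t and Cmax, for both analytes, lying within 80.00–125.00%. For the second stage, section 8.5 adds only the 94.12% interval with alpha 0.0294.

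**The concern.** Four comparisons must pass, but both numeric conditions for a second stage concern AUC_t, and the analyte is not named. Cmax enters only through the stage 1 verdict and through a probability judgement with no threshold. The size of stage 2 has a floor but no formula, target power or maximum. The power check in condition 1 does not state its assumed ratio.

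If Cmax is the likelier failure, condition 2 would be opened by a measure that its only number does not examine. Run at the minimum of 12, the added stage could be too small for the comparison that failed. Healthy women would then be dosed and sampled to little purpose.

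**Working it through.** **The plan's own figure.** 1 − 2 × 0.0294 = 0.9412, so the 94.12% level reproduces. No inputs are given for 24 or for 12.

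**Within-subject CVs from Tables I and II** (section 5.2; n = 30, balanced 2×2 assumed). SE = ln(upper/lower)/(2 × 1.7011), using t(0.95, 28). Then s² = 15 × SE² and CV = √(exp(s²) − 1).

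| Comparison | 90% CI (%) | Ratio (%) | SE | CV |
|---|---|---|---|---|
| EE AUC_t | 92.21–104.66 | 98.2 | 0.0372 | 14.5% |
| EE Cmax | 91.94–100.29 | 96.0 | 0.0256 | 9.9% |
| CPA AUC_t | 94.08–100.15 | 97.1 | 0.0184 | 7.1% |
| CPA Cmax | 86.23–97.63 | 91.8 | 0.0365 | 14.2% |

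These come from another test product, in "35 female postmenopausal healthy volunteers (aged 35-65 years"), so they are a guide only.

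**When AUC_t can fail inside the window.** With 12 per sequence, the section 8.5 formula gives SE = √(MS/12).

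- At ratio 0.90: ln(0.90/0.80)/1.7171 = 0.0686; MS = 12 × 0.0686² = 0.0565; CV = 24.1%.
- At ratio 1.10: ln(1.25/1.10)/1.7171 = 0.0744; MS = 0.0665; CV = 26.2%.

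An observed AUC_t CV below 24.1% cannot give this failure. At the worst true ratio its probability is 0.0004% at CV 14.5%, 0.4% at 20%, 5% at 25% and 14.5% at 30%. So Cmax would be the usual trigger unless AUC_t CVs are well above the published ones.

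**A comparison that just fails at n = 24, with 12 added.** Its margin is 1.717 stage 1 SEs. At N = 36 that is 1.717 × √(36/24) = 2.103 SEs, against t(0.9706, 33) = 1.957. Taking the observed ratio and CV as true:

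- Unconditional power is 56%.
- Conditional power is about Φ((2.103 − 1.957)/√(12/36)) = Φ(0.25) = 60%.
- The first total N with 80% power is 64, that is 40 added. For 80% conditional power, 30 added suffice (80.6%).

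**Simulation** (200,000 runs per scenario; correlation 0.6 within analyte; pooled analysis with a stage term; unlisted inputs at published values). The first figure in each cell uses the AUC_t window alone with exactly 12 added. The second uses an illustrative rule: conditional power of at least 50% on all four comparisons, the smallest sufficient addition of 12 or more, and a total of at most 72.

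| Scenario | Opens (% of trials) | Passes if opened (%) | Failed stage 2 (% of trials) | Rescued (% of trials) | Mean added per trial | Added per rescue |
|---|---|---|---|---|---|---|
| Published values | 5 v 4 | 77 v 95 | 1.2 v 0.2 | 3.9 v 3.6 | 0.6 v 0.8 | 15 v 22 |
| CPA Cmax ratio 1.146 | 33 v 18 | 39 v 77 | 20 v 4 | 12.8 v 13.9 | 4.0 v 4.2 | 31 v 30 |
| EE Cmax ratio 1.183, CV 9.9% | 43 v 22 | 35 v 73 | 28 v 6 | 15.1 v 16.5 | 5.2 v 5.3 | 34 v 32 |
| EE Cmax ratio 1.183, CV 15% assumed | 67 v 24 | 16 v 51 | 56 v 12 | 10.5 v 12.1 | 8.0 v 5.9 | 76 v 49 |
| All CVs 25% assumed | 35 v 22 | 39 v 73 | 22 v 6 | 13.6 v 15.8 | 4.2 v 4.9 | 31 v 31 |

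The last column is mean added divided by the rescue rate, for example 0.6/0.039 = 15. The first figures are upper bounds on openings, because they ignore the plan's requirement that success be probable.

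**Condition 1.** At n = 24, 80% power holds up to a CV of 16.0%, 23.2% or 26.0% for an assumed ratio of 0.90, 0.95 or 1.00. Using the largest of the four CVs, with ratio 0.95 and all CVs at 20%, would meet condition 1 in 24% of trials, against 15% on AUC_t alone.

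**The case for a change.** The strongest case for a change has three parts.

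- **Cmax is the likely trigger.** In the simulation no condition 2 opening at the published CVs involved an AUC_t failure. With all CVs at 25%, only 18% did (published ratios). The pilot points the same way: ratios of arithmetic means are 107.45/86.37 = 1.244 and 18.87/16.47 = 1.146 for Cmax (EE, CPA), against about 1.03 for AUC_t.
- **The judgement is made with results in hand.** Section 8.2.4 opens the code just before the statistical analysis, so the stage 1 results are known when continuation and size are chosen.
- **Each added woman bears a burden**, including 108 mL of blood per period (section 8.1.5), and the remedy is only wording.

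The first part stands as a description, up to CVs of about 25%; at 30%, 44% of openings involve AUC_t. The pilot adds little: it has six subjects, and its tables name the test product differently from the study product without saying whether the formulation is the same. The second part stands as a reason why a number would be tidier. It does not show that the decision would be made badly, since a team that knows Cmax failed must still find success probable on Cmax.

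The third part is not borne out. The large contrasts come from dropping the "probable" requirement and fixing the addition at 12, neither of which the plan does. The illustrative rule adds more subjects per trial on average in four of the five scenarios. Its own 50% threshold would also accept 12 added for a just-failing comparison (60% conditional power), so the floor is not plainly too small.

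**Conclusion.** No change follows. The rule is unquantified, but its text already reaches Cmax: a bioequivalence result means all four comparisons, and the addition can exceed 12. Analysts can fill the gap sensibly by checking conditional power on the failing comparison and sizing from it. Cmax remains in the final criterion, so this gap creates no false bioequivalence claim. Whether the interval levels at the two stages are adequate is a separate question.

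At the published ratios and CVs the cost is at most about 1.2% of trials with a failed second stage, against 0.2% under the illustrative rule. The larger differences (20–56% against 4–12%) need pilot ratios from six subjects or an assumed CV of 25%, and they are upper bounds.

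Putting a number on "probable" is a trade-off. A 50% threshold keeps rescues similar with larger second stages. An 80% threshold cut rescues from 12.7% to 6.7% in one re-run and from 13.6% to 8.5% in another, roughly 47% and 38%. Extending condition 1 to the largest CV would recruit more women after bioequivalence is already shown.

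The conclusion rests on reading "probable" by the plan's own definition of bioequivalence, and on Tables I and II being a fair guide to variability. The documents give no within-subject CV for this site or assay.

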8.1.1. Subject screening and selection

Subject screening and selection take place prior to the sampling period. Informed consent must be obtained from each subject before the screening process. Participation must be voluntary. All subjects will be informed of possible side effects and be advised that they are free to withdraw from the study at any stage. A subject information sheet and consent form in the subjects' first language will be provided.

The investigator informs all the subjects about the details of the study, i.e. the objective and the procedure, as well as the study rules to be followed during the study and the possible adverse effects of the drug.

Medical history, physical examination, laboratory tests (routine hematology, blood biochemistry and urinalysis), electrocardiograph, pregnancy test and HIV, HBsAg, and HCV tests are carried out to screen the subjects and to obtain eligible subjects who meet the inclusion and exclusion criteria.

The Study Coordinator or Study Physician takes subjects' demography data which include full name, sex, date of birth, age, address, race, height, weight, and smoking and alcohol consumption habit.

The medical history taken includes systemic review of allergies, family history, cramps or pain legs history and surgical history. Prior to physical examination and laboratory tests, the hormonal screening will be conducted to ensure that there is no interference with endogenous substance baseline levels.

The physical examination includes overall appearance, eyes, ears, nose, throat, head and neck, heart, lung, abdomen (including liver and spleen), lymph nodes, skin, musculoskeletal, and nervous system examination. The responsible physician will also examine if there is any sign of varices. The vital signs will also be measured, which include blood pressure, pulse, respiration rate and body temperature.

The laboratory tests cover complete hematology (hemoglobin, leucocyte, white blood cell differential counts, erythrocyte, platelet, hematocrite, and erythrocyte sedimentation rate), blood chemistry (alanine aminotransferase/ALT/SGPT, aspartate aminotransferase/AST/ SGOT, alkaline phosphatase, bilirubin, blood glucose level, ureum, and creatinine), and urinalysis (density, pH, leucocyte, nitrite, albumin/protein, glucose, ketone (acetone), urobilinogen, bilirubin, and blood count). A total of 15 mL of blood will be taken for the laboratory test.

Pregnancy test is carried out in screening process and on the day of sampling just before the drug administration. Women of childbearing potential are advised to take the necessary precaution to prevent pregnancy and to report to the Investigator or Study Physician if they suspect pregnancy.

The subjects are required to meet the inclusion and exclusion criteria. The screening data of all subjects will be evaluated and subjects with any current or past medical condition which may significantly affect the study results and assessment will be excluded from the study. Investigator or Responsible Physician judgment is required to determine subject's eligibility upon clinically insignificant abnormal results.

Inclusion criteria

The inclusion criteria are healthy female subjects who/with:

- have read the subject information and signed informed consent documents
- age 18 – 55 years
- body mass index between 18–25 kg/m²
- have a normal electrocardiogram
- blood pressure within normal range (90-120 mmHg for systolic blood pressure and 60-80 mmHg for diastolic blood pressure)
- heart rate within normal range (60-100 bpm)
- with absence of significant disease or clinically significant abnormal laboratory values on laboratory evaluation, medical history or physical examination during screening
- pass hormone screening related to cyproterone acetate and ethinyl estradiol

Exclusion criteria

Any of the following criteria will exclude the subject from the study:

- those who are pregnant and/or nursing woman.
- those with history of hypersensitivity to cyproterone acetate and ethinyl estradiol or other oral contraception or other ingredients in the drugs or a history of serious allergic reaction to any drug, significant allergic disease, allergic reaction, or active allergic.
- those with a history or presence medical condition which might significantly influence the pharmacokinetic of the study drug, e.g. chronic gastrointestinal disease, diarrhea, gastric surgery, renal insufficiency, hepatic dysfunction or cardiovascular disease.
- those with a history or presence of any coagulation disorder or clinically significant hematology abnormalities, thrombophlebitis, and thromboembolic disorder.
- those who are using any medication (prescription or non-prescription drug, food supplement, herbal medicine, oral contraception, anti-platelet drug), particularly the medication known to affect the pharmacokinetic of the study drug, within one week prior to the drug administration day.
- those who have participated in any clinical study within 3 months prior to the study (< 90 days).
- those who have donated or lost 300 ml (or more) of blood within 3 months prior to the study.
- those who smoke.
- those who are positive to HIV, HBsAg, and HCV tests (to be kept confidential).
- those with a history of drug or alcohol abuse within 12 months prior to screening for this study.
- those who are unlikely to comply with the protocol, e.g uncooperative attitude, inability to return for follow up visits, poor venous access.

8.1.2. Restriction

The subjects are instructed to abstain from taking any medication for at least one week before and during the study period unless it is medically necessary. If ingestion of any drug during the study is considered necessary, the Investigator has to be consulted and the drug has to be recorded (also its dose and time of administration) as a concomitant medication.

They are not permitted to smoke, consume alcohol, milk, beverages or food containing xanthines, such as tea, coffee, chocolate, cola, or fruit juice for 24 hours prior to the study day and the entire sampling day until the last blood sample is completely collected. The subjects have to avoid severe physical exertion during sampling hours.

On the evening before the study day, Study Physician will interview the subjects for the restriction compliance.

